The DMC will be responsible for review of the SAEs and AEs for each site and across the study as a whole. The DMC will make all decisions for stopping the study based on safety concerns, should any present. Early analyses before the study is completed may result in stopping of the study. For example, if it is statistically demonstrated that the results for either efficacy or futility to date could not be changed with further enrollment, the study may be stopped. When repeated significance tests are performed on accumulating data as part of a routine monitoring function, the overall type-I error rate is inflated and the probability of a false positive finding is also increased. A number of methods have been developed to provide guidance on study termination rules based on multiple looks at the primary outcome measures for the review committees while keeping the overall type-I error rate maintained at 5%. For this study, the O'Brien-Fleming method for alpha spending and rejection/acceptance boundaries will be suggested for Type-I error rate control (see Statistical Analysis Plan (SAP – Section XIII) for further details) but the DMC will make the final decision on the type of stopping rule that will be used for the study.

XII. QUALITY ASSURANCE PROCEDURES

Centralized and on-site reviews and monitoring of clinical site practices will be conducted at several levels. The National Coordinator will visit each site two times per year during the enrollment years to monitor the EAW Training, patient safety, and compliance with the study protocol. The Co-National Coordinator will visit each site one time annually during the enrollment years to monitor standardization of the QOL assessments and protocol compliance. Participant's medical records will be made available to the CSP Site visitors as a requirement for participation in this study.

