Sample size/power calculation for the Primary Outcome (2) SCI-QOL for Bladder, Bowel and Pain: An improvement of 10% in the sum T-score of the patient-reported outcomes from the combined SCI-QOL item banks for bladder management difficulties, bowel management difficulties and pain interference is clinically significant. As such, it is hypothesized that 42% of the Intervention group compared with 10% of the Control group will demonstrate a clinically significant change of 10% improvement from baseline to the end of the intervention phase on the sum T-score in the combined SCI-QOL item banks for bladder management difficulties, bowel management difficulties and pain interference. (Table 7).

Sample size/power calculation for the Major Secondary Outcome for Total Body Fat Mass: Patients with a new SCI can be expected to gain an average of 6.0 ± 8.9 kg of fat mass in the first 14 months after injury (manuscript in preparation from our Center). This gain in fat mass appears to continue throughout the duration of their life after SCI. As demonstrated in the preliminary data, an intervention that supports a 1.0 kg (2.2 lb.) loss of fat mass is a substantial amount of fat mass to lose in three months for a person with SCI. Very few interventions have demonstrated changes in body composition of this magnitude in the SCI population. It is expected that 35% of the Intervention group compared with 10% of the Control group will maintain total body fat mass loss during the home/community use phase of the intervention.

Assuming the proportion in the control group achieving a clinically meaningful change to be 10% (or 0.100) for all three outcome measures, and estimating the attrition rate at 15%, the sample sizes range from a low of 71 per group (95% power) for the SCI-QOL PMH outcome to a high of 79 per group (80% power) for the MCS/VR-36 group. As a note about Table 7, to adjust for multiple outcome measures, a significance level of 0.025 was used in the sample size calculations for the co-primaries (MCS/VR-36 and SCI-QOL) and also for the major secondary outcome measure (Total Body Fat Mass). Based on the sample size and power calculations in Table 7, the study will enroll a total sample size of 160 participants, 80 per group.

Table 7: Sample Size/Power Calculations			
Two group continuity corrected χ^2 test of equal proportions (odds ratio = 1) (equal n's)	MCS/VR-36	SCI-QOL (PMH)	Total Body Fat Mass
Test significance level, α	0.025	0.025	0.025

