In addition to the tables for the reports, the computer auditing system produces Quality Control (QC) reports that indicate the number of errors that were found on the individual forms. QC reports that are overly large will identify those sites requiring additional training on forms completion. A

monthly report summarizing data submission and problem identification for each site will be sent to the Study Chairperson so that she can monitor how the participating sites are doing.

Table 12. CS #2003 Number of Missing Forms by Site

# of Participants		Site				Total
		1	2	...	15	
Form 01	N					
	%					
Form 02	N					
	%					
.						
.						
.						
Form X	N					
	%					

I. Study Monitoring by the Data Monitoring Committee (DMC)

An independent oversight committee called the Data Monitoring Committee (DMC) will monitor study progress. This committee meets on the same basic schedule as the Study Group and Executive Committee, i.e., they will meet at 6 to 9 months after the start of patient recruitment and yearly thereafter. This committee does not usually meet during the last six months of a study. They will also meet once prior to the study startup to acquaint themselves with the study and to establish their procedures for reviewing and monitoring the study.

The major responsibility for the DMC members when they meet is to make a recommendation to the Director of the Cooperative Studies Program as to whether or not the study should continue. The study could be recommended for termination due to poor recruitment, treatment differences so large that it is possible to reach a final decision or treatment differences so small that continuation would be irresponsible. The DMC also reviews the participating sites’ performance and makes recommendations concerning them. Data collected during the feasibility phase of the study, including site performance, verification of success rates in the control group and other operational measures, will be presented to the committee for its review and recommendations. Their final responsibility is to review all proposed protocol changes and sub-protocols and to make recommendations about their acceptability.

For the DMC to carry out its responsibilities, the CSPCC Study Team will provide the committee with a report approximately three weeks prior to their meetings. The report will consist of the tables described previously for the Study Group and Executive Committee reports as well as those

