For the DMC to make its recommendation for continuation of the study, it will be necessary for them to see the analysis of the primary and major secondary outcome measures every time they are provided a report of study progress and it is possible to calculate these measures. Periodic monitoring of interim results can significantly affect the probability of making an incorrect decision (Type-I error rate). One interim look at the primary outcome measures (in addition to the final “look” at study’s end) will be proposed to the DMC for making the recommendation about whether or not to continue the trial or to stop for early efficacy. It is proposed that the one look occur when 80 (50%) patients have completed participation in the study. The O’Brien-Fleming method for alpha spending and rejection/acceptance boundaries will be suggested for Type-I error rate control. The O’Brien-Fleming boundaries for rejection (α) and acceptance (β) as well as the Type-I error rates for the two looks are given in Tables 15 and 16 for the MCS/VR-36 and SCI-QOL/PMH outcomes, respectively. The boundaries are presented graphically in Figures 10 and 11 for the two primary outcome measures.

Table 15. CS #2003: Two-sided O’Brien-Fleming Boundaries for Rejection (α) and Acceptance (β) – MCS/VR-36

Interim Look (Stage)	No. of Randomized Participants	Std. z (Rejection)		Std. z (Acceptance)		Type-I error
		Lower	Upper	Lower	Upper	
1	80	-3.12376	3.12376	-0.88945	0.88945	0.00089
2	160	-2.20883	2.20883	-2.20883	2.20883	0.01250

Figure 10. CS #2003 Combined Boundary Plot for MCS/VR-36

[figure not shown]
[figure not shown]

Table 16. CS #2003: Two-sided O’Brien-Fleming Boundaries for Rejection (α) and Acceptance (β) – SCI-QOL Physical Medical Health (PMH) domain

Interim Look (Stage)	No. of Randomized Participants	Std. z (Rejection)		Std. z (Acceptance)		Type-I error
		Lower	Upper	Lower	Upper	
1	80	-3.16956	3.16956	-0.40071	0.40071	0.00076
2	160	-2.24122	2.24122	-2.24122	2.24122	0.01250

Figure 11. CS #2003 Combined Boundary Plot for SCI-QOL Physical Medical Health (PMH) Domain

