QOL outcome assessments (VR-36, SCI-QOL, Global Impression of Change Scale (Participant- and Companion-rated), PROMIS Sleep Disturbance, SCI-FI, and bowel function surveys) will be completed by each participant during an in-person or phone interview by a member of the study site staff. The interviewer will record the answers, making sure that all questions are answered. This data will be sent to the CSPCC via a Datafax system.

XVII. PLANS FOR DISSEMINATION OF STUDY RESULTS

A. Publication of Research Results

It is the policy of the Cooperative Studies Program not to reveal outcome data to Site Investigators until the data collection period of the study is complete. This policy is meant to prevent possible biases that might affect data collection. Members of the DMC will be reviewing outcome results to ensure that the study will be terminated early if a treatment is identified as prohibitively dangerous or if a definitive answer is reached prior to the scheduled study termination date.

All presentations and publications resulting from this study will follow CSP policy as specified by the CSP guidelines. The presentation or publication of any or all data collected by Site Investigators on patients entered into a Department of Veterans Affairs Cooperative Study is under the direct control of the study's Executive Committee. No individual Site Investigator has the right to use the study's data to perform analyses or interpretations, or to make public presentations or seek publication of any or all of the data without specific approval of the Executive Committee.

The Executive Committee has the authority to establish any number of publication committees, which usually will comprise of subgroups of Site Investigators and some members of the Executive Committee, for the purpose of producing manuscripts for presentation and publication. Any presentation or publication related to this study should be circulated to the Executive Committee for review, comments and suggestions at least four weeks prior to submission of the manuscript to

the presenting or publishing body.

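### The interim boundaries deliver 0.025 per primary only if acceptance is binding for each outcome, which the plan does not state; if it is binding, MCS power falls below the 80% of Table 7.

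*Combined protocol and SAP*

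**What the plan says.** Sections XIII.B and XIII.E give each of the two primaries a two-sided level of 0.025. Section XIII.F compares success proportions by a chi-square test, with drop-outs counted as failures. Neither E nor F refers to the interim boundaries.

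Section XIII.I proposes one look when 80 of 160 participants have completed, for "making the recommendation about whether or not to continue the trial or to stop for early efficacy". It says that O'Brien-Fleming "rejection/acceptance boundaries will be suggested for Type-I error rate control". The printed values are:

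| Outcome | Interim reject, \|z\| ≥ | Interim accept, \|z\| < | Final \|z\| | Type I error (interim; final) |
|---|---|---|---|---|
| MCS/VR-36 (Table 15) | 3.12376 | 0.88945 | 2.20883 | 0.00089; 0.01250 |
| SCI-QOL PMH (Table 16) | 3.16956 | 0.40071 | 2.24122 | 0.00076; 0.01250 |

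Futility is otherwise described for the study as a whole and in permissive terms. Section XI.J says that if results for efficacy or "futility to date could not be changed with further enrollment, the study may be stopped", and adds that "the DMC will make the final decision on the type of stopping rule that will be used for the study". Section XIII.I lists, among possible grounds for recommending termination, "treatment differences so small that continuation would be irresponsible". Section XVII.A speaks of ending the study early "if a definitive answer is reached prior to the scheduled study termination date".

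Table 7 sizes the trial with a "Two group continuity corrected" chi-square test, at 80% power for MCS and 95% for SCI-QOL. It makes no allowance for an interim look.

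**The concern.** With no interim look, a two-sided 0.025 test needs |z| ≥ 2.2414. Adding a look with a chance to stop for efficacy should push the final cut-off above that value. Table 15 puts it below, at 2.20883. The only thing that can pay for this is a bar on later rejection once MCS has fallen in its acceptance zone at the interim.

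The plan does not state such a bar. The boundaries are set per outcome, but stopping is described per study. If MCS lies in its acceptance zone and the trial continues for SCI-QOL, nothing says whether MCS may still be tested at the end. One reading gives up MCS power that Table 7 promises; the other gives up some of the printed error control. An analyst working from XIII.E would use p < 0.025, and one working from Table 15 would use p < 0.0272.

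**Working it through.** **Inputs.** Boundaries from Tables 15 and 16; information fraction 80/160 = 0.5; two-sided alpha 0.025 per primary (XIII.B, XIII.E); success rates 10% against 33.3% (MCS) and 10% against 42% (SCI-QOL), with 15% attrition (Table 7).

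**Model.** Z1 and Z2 are the interim and final statistics, with correlation √0.5. With drift θ at the final analysis, E(Z1) = θ√0.5 and E(Z2) = θ. Upper-tail rejection probability:
- acceptance enforced: P(Z1 ≥ c1) + P(a1 ≤ |Z1| < c1, Z2 ≥ c2);
- acceptance ignored: P(Z1 ≥ c1) + P(|Z1| < c1, Z2 ≥ c2).

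**1. Reproducing the plan's type I error (θ = 0).**

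| | Interim, per tail | Cumulative per tail, enforced | Two-sided, enforced | Two-sided, ignored |
|---|---|---|---|---|
| MCS | 0.00089 | 0.01250 | 0.0250 | 0.0279 |
| SCI-QOL | 0.00076 | 0.01250 | 0.0250 | 0.0256 |

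The printed figures are matched only with acceptance enforced. Under the null, MCS falls in its acceptance zone at the interim with probability 2Φ(0.88945) − 1 = 0.626.

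**2. Nominal power.** The Table 7 drift is z(0.9875) + z(power): 2.2414 + 0.8416 = 3.083 for MCS and 2.2414 + 1.6449 = 3.886 for SCI-QOL.

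| | No interim | Tables, enforced | Tables, ignored | Efficacy-only pair |
|---|---|---|---|---|
| MCS | 80.0% | 77.9% | 81.0% | 79.8% |
| SCI-QOL | 95.0% | 94.7% | 95.0% | 94.9% |

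Table 15 itself implies a larger drift. C_β = 2.20883 − 0.88945/√0.5 = 0.951, and 2.20883 + 0.951 = 3.160 is the drift at which the binding design has 80% power. The information ratio is (3.160/3.083)² = 1.050. Applied to Table 7, 67 × 1.050 = 70.4, so 71 per group, and 71/0.85 = 83.5, so 84 randomized per group against 80 planned.

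**3. Efficacy-only pair.** Solve for c with interim c/√0.5 and final c, acceptance ignored, two-sided error 0.025. This gives c = 2.2505: interim 3.183, final p 0.0244.

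**4. Exact binomial error with acceptance ignored** (full enumeration, 40 then 80 per arm, common success rate in both arms):

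| Null rate | MCS, Pearson | SCI-QOL, Pearson | MCS, continuity-corrected |
|---|---|---|---|
| 8.5% (10% × 0.85) | 0.0250 | 0.0208 | 0.0108 |
| 10% | 0.0260 | 0.0219 | 0.0119 |
| 15% | 0.0278 | 0.0246 | 0.0146 |

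At 10% the two Pearson rates sum to 0.0260 + 0.0219 = 0.0479, which bounds the family-wise error at any correlation between the outcomes. With acceptance enforced, the exact MCS error at 10% is 0.0235 (Pearson) or 0.0103 (corrected).

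**5. Exact MCS power** at 80 per arm, drop-outs as failures (0.10 × 0.85 = 0.085 against 0.333 × 0.85 = 0.283):

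| | No interim | Tables, enforced | Efficacy-only pair |
|---|---|---|---|
| Pearson | 86.5% | 84.8% | 86.5% |
| Continuity-corrected | 81.0% | 77.6% | 80.9% |

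**The case against.** The strongest reply is that the tables already answer the question. They print acceptance boundaries, offer them for type I error control, and give errors that hold only if acceptance is enforced. The interim sentence also asks whether or not to continue, so it does not limit the look to efficacy. This stands: enforcement is the only reading consistent with the printed errors. It still does not say what happens to an accepted outcome when the trial runs on for the other primary, and it leaves the power cost unstated.

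A second reply is delegation. The boundaries are proposals, and the DMC meets before start-up "to establish their procedures for reviewing and monitoring the study". Those procedures may settle the matter and are not part of this document. The final critical value depends on them, however, and XIII.E and F fix a level without reference to them.

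A third reply is that the error excess is close to nil, and on exact figures it is. If the final test is run at |z| ≥ 2.2414, as XIII.E implies, exact Pearson MCS error with acceptance ignored is 0.0208, 0.0220 and 0.0249 at null rates of 8.5%, 10% and 15%. The exact 0.0278 needs a 15% null rate, and XIII.C regards a control rate above 10% as highly unlikely.

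A reader might infer that the boundaries are miscalculated or that the trial's 5% error is breached. Neither is supported: the tables are correct as a binding design, and the Pearson bound at the planned 10% rate is 0.0479.

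**Conclusion.** The point holds as a minor one. As written, the plan delivers either the printed type I error or the Table 7 MCS power, but not both, and it does not say which. Enforcing acceptance costs MCS about 2 points of nominal power (80% to 77.9%); in exact terms 1.7 points with Pearson (86.5% to 84.8%) or 3.4 with the correction (81.0% to 77.6%). Ignoring acceptance with the printed cut-offs raises MCS error to 0.0279 by normal theory and 0.0260 by exact Pearson at a 10% null rate, with no excess under the continuity correction. For SCI-QOL the effect is negligible either way. At the planned MCS effect the two readings differ in 81.0 − 77.9 = 3.1% of trials.

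The exact results assume the interim falls at 40 per arm; the exact power figures also assume 15% drop-out in both arms. The 77.9% is a nominal figure scaled to exactly 80% and should not be read as this trial's power.

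Primaries that disagree at the interim are a secondary gap. Under the planned effects, exactly one crosses its rejection boundary in 39%, 33%, 29% and 24% of trials at correlations of 0, 0.3, 0.5 and 0.7. These correlations are assumed, because the documents give none.

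**What to change.** **Preferred.** Replace Tables 15 and 16 with one efficacy-only O'Brien-Fleming pair for both primaries: |z| ≥ 3.183 at the interim and |z| ≥ 2.250 (p 0.0244) at the end. Label any acceptance boundary non-binding and cite that final level in XIII.E and XIII.F. By normal theory this holds 0.025 per primary whatever the DMC does about acceptance. It costs about 0.2 points of nominal MCS power, no change in sample size, and an edit to the SAP text.

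**If the tables are kept.** State that acceptance binds for each outcome, including when the trial continues for the other primary. Restate MCS power for the actual sample size and for the chi-square version that will be used.

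**If the look has already taken place.** Use the final value that matches the rule the DMC recorded before the look. For MCS that is 2.20883 if acceptance was binding, or 2.253 (p 0.0243) if it was not; for SCI-QOL, 2.24122 or 2.251 (p 0.0244). If no rule was recorded, use the stricter value, so that the cut-off is not chosen after the data.

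In every case, name the chi-square version, cite the DMC procedures if they already cover this, and add a sentence on what happens when only one primary crosses a boundary.
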